Appendix
(photos)

APPENDIX 2

PARENT SURVEY

Subject ID:

() Mother () Father () Other: _____

Section 1: Your experience with the Wired Monitoring

1. How satisfied are you with the system?
 - a. Very dissatisfied
 - b. Dissatisfied
 - c. Neutral
 - d. Satisfied
 - e. Very satisfied

1. What are your concerns? (Mark all that apply - multiple choices are permitted)
 - a. Problems with the stickers on my baby's skin
 - b. Too many stickers on my baby's skin
 - c. Too many wires around my baby
 - d. Difficult to touch my baby because of the stickers and wires
 - e. The stickers, wires and monitors are concerning
 - f. No concerns
 - g. Other (please specify): _____

1. The monitors and wires interfere with my ability to do skin-to-skin (Kangaroo) care:
 - a. Strongly disagree
 - b. Disagree
 - c. Neutral
 - d. Agree
 - e. Strongly agree

1. What kind of problems have you seen with the use of the wired monitoring system? (Mark all that apply - multiple choices allowed)
 - a. Skin lesions associated with chest adhesives
 - b. Skin lesions associated with the limb probe
 - c. Pressure sore associated with chest adhesives
 - d. Pressure associated with the limb probe
 - e. Fear of handling my baby because of the multiple wires and cables
 - f. Wires tangled around the baby chest or limbs
 - g. Wires soiled – requiring replacement or cleaning
 - h. Cables soiled – requiring replacement or cleaning
 - i. Installation time
 - j. Wires disconnected
 - k. Cables disconnected

I. Other:

1. The adhesives, sensors, wires, and monitors, can prevent me from bonding with my baby:
 - a. Strongly disagree
 - b. Disagree
 - c. Neutral
 - d. Agree
 - e. Strongly agree

Section 2: Your experience with the Wireless Monitoring

1. What is your opinion about the use of a new wireless technology to monitor your baby's vital signs?

Chest sensor

- a. Strongly oppose
- b. Somewhat oppose
- c. Neutral
- d. Somewhat favor
- e. Somewhat favor
- f. Strongly favor

Limb sensor

- a. Strongly oppose
- b. Somewhat oppose
- a. Neutral
- c. Somewhat favor
- d. Somewhat favor
- e. Strongly favor

1. I am worried about the safety and the accuracy of the new wireless technology.

Chest sensor

- a. Strongly disagree
- b. Disagree
- c. Neutral
- d. Agree
- e. Strongly agree

Limb sensor

- a. Strongly disagree

- b. Disagree
- a. Neutral
- c. Agree
- d. Strongly agree

1. What are your main concerns with the implementation of a new wireless technology in the Delivery Room? (Mark any that apply - multiple choices permitted)

Chest Sensor

- a. Accuracy (good and reliable data)
- b. Challenges using sensors
- c. Safety of stickers used to apply sensors
- d. Size of the sensors
- e. Weight of the sensor
- f. Battery life of wireless sensors
- g. No concerns
- h. Other (please specify):

Limb Sensor

- a. Accuracy (good and reliable data)
- b. Challenges using sensors
- c. Safety of stickers used to apply sensors
- d. Size of the sensors
- e. Weight of the sensor
- f. Battery life of wireless sensors
- g. No concerns
- h. Other (please specify):

1. What do you think might be the impact of a wireless system on bonding between parents and their babies?

- a. Strongly negative
- b. Negative
- c. Neutral
- d. Positive
- e. Strongly positive

1. What do you think might be the impact of a wireless system on your baby's hospital experience? (Mark any that apply - multiple choices permitted)

- a. Easier Kangaroo care (KC) initiation
- b. Increase the amount of time on KC
- c. Reduce discomfort

- d. Decrease pain
- e. Better sleep
- f. Newborn safety
- g. None
- h. Other (please specify):

1. Any additional comment (s):

DO NOT COPY

HEALTH CARE PROFESSIONAL'S SURVEY

Subject ID:

() Neonatologist () Neonatal Fellow () Pediatric Resident

() Registered Nurse () Neonatal Nurse Practitioner

() Respiratory Therapist

() Other: _____

Years of experience: () < 2 years () 2-5 years () 6-10 years () > 10 years

Section 1: Current State of Monitoring with Wires and Cables

1. How satisfied are you with the use of monitoring system with wires and cables immediately after birth and up to 2h of age in the DR?

- a. Very dissatisfied
- b. Dissatisfied
- c. Neutral
- d. Satisfied
- e. Very satisfied

2. What are your main concerns with the monitoring system with wires and cables? (Mark any that apply - multiple choices permitted)

- a. Inaccurate readings
- b. False alarms
- c. Issues associated with adhesion of the sensors (heat generation or pressure and skin irritation)
- d. Too many sensors applied to the skin
- e. Too many wires around the baby
- f. Difficult to handle the baby because of the multiple wires and cables
- g. The sensors, wires and cables are intimidating to the parents
- h. I do not have concerns
- i. Others (please specify): _____

3. What are the main benefits of using a wired and cable monitoring system immediately after birth and up to 2h of age in the DR? (Mark any that apply - multiple choices allowed)

- a. Easy to use
- b. Various functions in this system were well integrated
- c. Quickly to learn how to use
- d. Fast speed of data display
- e. There are no benefits

f. Others (please specify):

4. How confident are you with the use of monitoring system with wires and cables immediately after birth and up to 2h of age in the DR?

- f. Not confident
- g. Somewhat not confident
- h. Neutral
- i. Somewhat Confident
- j. Confident

5. What kind of problems did you see by using the current standard monitoring system in healthy babies immediately after birth and up to 2h of age in the DR? (Mark any that apply - multiple choices permitted)

- a. Skin lesions associated with ECG adhesives
- b. Skin lesions associated with the oxygen saturation sensor
- c. Pressure sores associated with ECG adhesives
- d. Pressure sores associated with the oximeter sensors
- e. Parents afraid to handle their baby because of the multiple wires and cables
- f. Wires tangled around the baby's chest or limbs
- g. Wires soiled – requiring replacement or cleaning
- h. Cables soiled – requiring replacement or cleaning
- i. Wires disconnected
- j. Cables disconnected
- k. Other:

6. List any other perceived benefits and disadvantages of the system:

Section 2: Wireless Monitoring System in the Delivery Room

7. What is your attitude towards the use of this new wireless chest sensor technology in the Delivery Room?
 - a. Very skeptical
 - b. Skeptical
 - c. Neutral
 - d. Optimistic
 - e. Very optimistic
8. What is your attitude towards the use of this new wireless limb sensor technology in the Delivery Room?
 - a. Very skeptical
 - b. Skeptical
 - c. Neutral
 - d. Optimistic
 - e. Very optimistic
9. What is your level of concern regarding the safety and accuracy of using this new wireless chest sensor technology, immediately after birth and up to 2h of age in the DR?
 - a. Very concerned
 - b. Somewhat concerned
 - c. Neutral
 - d. Somewhat concerned
 - e. Not concerned at all
10. What is your level of concern regarding the safety and accuracy of using this new wireless limb sensor technology, immediately after birth and up to 2h of age in the DR?
 - a. Very concerned
 - b. Somewhat concerned
 - c. Neutral
 - d. Somewhat concerned
 - e. Not concerned at all
11. What are your main concerns, if any, with the implementation of this new wireless technology in the Delivery room, regarding the chest sensor? (Mark any that apply - multiple choices permitted)
 - a. Accuracy (good and reliable data)
 - b. Challenges related to “user-friendliness” of technology
 - c. Safety
 - d. Size of the sensors
 - e. Weight of the sensor

- f. Battery life
- g. Radio frequency radiation
- h. Other (please specify):

12. What are your main concerns, if any, with the implementation of new wireless technology in the Delivery room, regarding the limb sensor? (Mark any that apply - multiple choices permitted)

- a. Accuracy (good and reliable data)
- b. Speed of data display
- c. Challenges related to “user-friendliness” of technology
- d. Safety
- e. Size of the sensors
- f. Weight of the sensor
- g. Battery life
- h. Radio frequency radiation
- i. Other (please specify):

13. What do you think it might be the impact of a using a wireless system immediately after birth and up to 2h of age in the DR, on some outcomes?

- a. Improve kangaroo care (KC) experience
- b. Increase the amount of time on KC
- c. Reduce discomfort
- d. Decrease pain
- e. Better sleep
- f. Newborn safety
- g. None
- h. Other (please specify):

14. Any additional comment (s)?:

APPENDIX 3

Neonatal Skin Condition Score (NSCS)

Dryness	Score
1 = Normal, no sign of dry skin.	
2 = Dry skin, visible scaling.	
3 = Very dry skin, cracking/ fissures.	
Erythema	
1 = No evidence of erythema.	
2 = visible erythema, <50% body surface.	
3 = Visible erythema, > 50% body surface.	
Break down/Excoriation	
1 = None evident.	
2 = Small, localized areas.	
3 = Extensive	
TOTAL SCORE	

Directions for Use:

- To identify a Neonatal Skin Condition Score (NSCS), choose the description that best fits the neonate's skin related to dryness, erythema, and break down / excoriation and assign the number most appropriate per description.
- Each section is given a score from 1 to 3.
- The "perfect" score using the NSCS is 3; the worst score is 9.

APPENDIX 4

Neonatal Infant Pain Scale(NIPS)

The NIPS (Lawrence et al., 1993)

Pain Assessment Tools
Neonatal/Infant Pain Scale (NIPS)

(Recommended for children less than 1 year old) - A score greater than 3 indicates pain

Pain Assessment		Score
Facial Expression		
0 – Relaxed muscles	Restful face, neutral expression	
1 – Grimace	Tight facial muscles; furrowed brow, chin, jaw, (negative facial expression – nose, mouth and brow)	
Cry		
0 – No Cry	Quiet, not crying	
1 – Whimper	Mild moaning, intermittent	
2 – Vigorous Cry	Loud scream; rising, shrill, continuous (Note: Silent cry may be scored if baby is intubated as evidenced by obvious mouth and facial movement.	
Breathing Patterns		
0 – Relaxed	Usual pattern for this infant	
1 – Change in Breathing	Indrawing, irregular, faster than usual; gagging; breath holding	
Arms		
0 – Relaxed/Restrained	No muscular rigidity; occasional random movements of arms	
1 – Flexed/Extended	Tense, straight legs; rigid and/or rapid extension, flexion	
Legs		
0 – Relaxed/Restrained	No muscular rigidity; occasional random leg movement	
1 – Flexed/Extended	Tense, straight legs; rigid and/or rapid extension, flexion	
State of Arousal		
0 – Sleeping/Awake	Quiet, peaceful sleeping or alert random leg movement	
1 – Fussy	Alert, restless, and thrashing	

APPENDIX 5

Neonatal Resuscitation within the Birthing Centre Working Protocol

Identification of cases or situations when to call 'NICU'

The goal is to anticipate any identifiable situation that may require neonatal resuscitation team presence prior to the delivery of the newborn in a timely fashion.

The neonatal resuscitation team is composed of neonatologist, respiratory therapist, NICU resuscitation nurse and NICU on call personnel (nurse practitioner, NICU pediatric resident, fellow or clinical assistant) and their spectralink numbers are listed as follows:

Neonatologist- [name]

NICU on call personnel- [name]

Respiratory therapist- [name]

NICU Resuscitation nurse- [name]

*NICU fellow may be called at [name] depending on the availability.

Role within the Birthing Centre

One professional within the birthing center needs to be assigned to each baby to be born. This person needs to be able to initiate resuscitation as per NRP guidelines.

If a situation is identified prior to labor, during labor and delivery or after birth that will require the presence of resuscitation team, the nurse taking care of the mother should call the NICU team member at " [name]. The nurse should be able to pass on the information regarding the situation, background information on the pregnancy and the presence of any complication, mode of delivery, level of urgency along with anticipated level of priority to the NICU covering person. Based on the priority level, the NICU person will mobilize the rest of resuscitation team members (i.e. RT, Resuscitation nurse or neonatal attending). Please see below the priority level, required neonatal staff and indications. In the event an emergency situation arises that will require emergent resuscitation of the newborn, the OB team members should press the "**code pink button**" in the labor room. The code pink button is linked to the spectralink numbers of the resuscitation team members.

"Code Pink"- may be called when a fetus or a neonate has a **perceived potential or documented need** for resuscitation. This may include, but is not limited to apnea or bradycardia unresponsive to stimulation, ineffective respiration or gasping with or without bradycardia, cyanosis, cardiac arrest or delivery of a neonate not making

appropriate transition and needing urgent intervention and supportive care. Unexpected delivery of a newborn outside the birthing center – warrants a code pink.

Level of Priority and Required Neonatal Staff

Priority 1: Pediatric resident/ NNP/ clinical assistant or fellow on call, NICU resuscitation nurse, neonatal RT, and neonatologist on call

Priority 2: Pediatric resident/NNP/clinical assistant or fellow on call, NICU resuscitation nurse and neonatal RT

“Code Pink” – Pediatric resident/NNP/ clinical assistant or fellow on Call, NICU resuscitation nurse, RT and neonatologist

ISBAR Communication Tool for Calling

Neonatal Resuscitation Team

NEONATAL RESUSCITATION

Identification	Identify yourself
Situation	
 ✓ Why is neonatology being called? ✓ Briefly state the problem, what it is, when it started, and how severe
Background	
 ✓ Gestational age ✓ Prenatal complications, presence or absence of ✓ Major anomalies ✓ Labor complications, fetal heart rate category ✓ Membranes: 
 Intact, ruptured Fluid: clear, cloudy, meconium
Assessment	
 ✓ Level of risk to the baby ✓ Plan for delivery: 
 Vaginal or C-section, level of urgency
Recommendation	
 ✓ Categorize level of priority level anticipated, inform the neonatal resuscitation team ✓ Specify the location of delivery

Indications for NICU Presence at Delivery		

Code Pink (press code pink button)
 
Neonatologist : [name]
 
NICU on call: [name]
 
RT: [name]
 
Res Nurse:[name]
 
Fellow: [name]*
	
NICU resident/NNP/clinical assistant or fellow on call
 
NICU resuscitation nurse
 
Neonatal RT
 
Neonatologist
 
*Denotes presence on availability
	
 • A fetus or neonate has a perceived potential or documented need for emergent resuscitation. • Unanticipated delivery in the antepartum unit on D-6 or outside birthing center

Priority 1
 
Call NICU on Call first at [name]
	
NICU resident/NNP/clinical assistant or fellow on call
 
NICU resuscitation nurse
 
Neonatal RT
 
Neonatologist
	
 • Preterm delivery < 32 weeks • Delivery of any newborn expected to require full resuscitation (vasa previa, cord prolapse, placental abruption, uterine rupture, fetal anemia) • The presence of fetal malformation with the potential of needing neonatal resuscitation (heart, lung, abdominal, cranio-facial or any other potentially impairing breathing) • Hydrops • Delivery of a fetus of questionable viability


Priority 2
 
Call NICU on Call first at [name]
	
NICU resident/NNP/clinical assistant or fellow on call
 
NICU resuscitation nurse
 
Neonatal RT
 
± Neonatologist
	
 • • Preterm delivery; GA 32-35 weeks • Stat, Priority 1 C-section • Severe oligohydramnios or polyhydramnios • Newborn unexpectedly receiving positive pressure ventilation (hypotonic with decreased respiratory effort-) • Multiple birth < 35 weeks GA • Oligohydramnios and the presence of other anomalies • Non reassuring fetal heart tracing - severe decelerations • Multiple birth > 35 weeks • Chorioamnionitis (maternal fever >38.0°C with two of the following findings: fetal tachycardia, maternal tachycardia, foul smelling discharge, uterine tenderness, leukocytosis WBC >15 000) • Shoulder dystocia • Meconium staining of amniotic fluid • Respiratory distress (abnormal breathing) at birth • General anesthesia • Maternal BMI > 40 • Any other issue at the discretion of the LDR nurses/OB Physician/Anesthesiologist • Baby more than 35 weeks of gestation but less than 2300 grams • Unexpected finding that does not require resuscitation • Instrumental delivery/vaginal breech delivery • Maternal narcotic administration within 2 hours of delivery
---	---	---

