3.3.3 Study Interventions

Each newborn enrolled in the Study will be monitored simultaneously by both the standard of care (control) wired vital sign monitoring system (Infinity M540 monitor, Draeger, Germany) and the wireless monitoring system (intervention) (ANNE Arc chest sensor, SIBEL Health, Illinois, USA and Limb sensor (RAD7, Masimo) (Figure 9).

Both monitoring systems, will simultaneous record heart rate, respiratory rate, oxygen saturation, and skin temperature for the first 2h of age.

Figure 9. Monitoring systems – ECG and temperature

Figure 10. Monitoring Systems – SpO2

All materials and equipment required for the conduct of the study will be provided to the participating sites by the lead site. All research team members at all sites will be trained on the placement and removal of the wireless and wired monitoring including appropriate cleaning and disinfecting protocols. Training on the use of the BioDash system will also be provided as part of the study training at all sites.

Vital Sign Monitoring:

If a baby is born via:

1. *Vaginal Delivery:* Following normal, vaginal delivery, the wireless skin sensor monitoring system (Anne Arc & RAD7 Limb,Sibel Health Inc - Masimo) will be immediately placed on the newborn. In order to promote the standard practice of bonding between newborn and mother the standard of care wired monitoring system (Infinity Monitor, Drager) will be placed on the newborn after 10-20 min of age.
2. *C-section:* Immediately before birth, the infant will be randomized for the type of monitoring system to be applied first: a) the wireless sensors (Anne Arc & RAD7 Limb,Sibel Health Inc - Masimo) or b) standard of care wired system (Infinity Monitor, Drager). In order to promote the standard practice of bonding between newborn and mother the second monitoring system will be placed on the newborn after 10-20 min of age.

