- Skin Pigment: Previous research has highlighted the challenges of some pulse oximeters in providing accurate readings for skin with darker pigmentation and as a result has emphasized the need to investigate the performance of pulse oximeters for different skin tones^{38,39}. The infant's skin color will be recorded using the adapted Munsell System Soil Color Chart (2009 Revision, Munsell Color, Grand Rapids, Michigan), Hue7.5YR to investigate impact of skin pigmentation on pulse oximetry accuracy. This scale has previously been used in research on neonates⁴⁰.
- *Pain Assessment*: As well, neonatal pain will be assessed throughout the sensor removal process. The pain scale (NIPS) will be completed by the study team member at the time of sensor removal and entered into REDCAP.
 - Neonatal Infant Pain Scale (NIPS)³⁶ : At the time of device removal, the researcher will complete the NIPS to ensure removal of adhesive does not cause significant discomfort to the patient. The scale consists of 6 items. Scores range from 0 to 7, with scores greater than 3 indicating presence of pain. This scale has been widely validated for the assessment of acute pain in neonates. This scale will be included in the Data Collection Form.
- *Surveys*: In order to assess feasibility on the use of wireless sensors to monitor babies after birth, a survey will be conducted to get the opinions of parents and Health Care Professionals involved in the care of the baby and mother. The survey will be presented in hard copy form as well as through REDCAP.
 - Parent Survey: Parents of the participating infant will be asked to complete a short survey to after the sensors of both systems are removed. The survey will be coded with the study code assigned to the participating infant, no personal health information or personal information will be asked of the parent for the completion of the survey. (See Appendix 2).
 - Health Care Professional Survey: HCPs involved in the care of the infant and mother after birth will be asked to complete a short survey after the sensors of both systems are removed in order to assess how the HCPs felt about the wireless skin sensors as compared to their experience of the standard of care wired monitoring system. (See Appendix 2).

REDCAP

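### Parents rate the wired and wireless systems once, after both were worn together for most of the 2 h, so the general items in the parent survey cannot be cleanly assigned to one system

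*Combined protocol and SAP*

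**What the plan says.** **Wear.** Section 3.3.3 puts both systems on every infant: "Each newborn enrolled in the Study will be monitored simultaneously by both the standard of care (control) wired vital sign monitoring system", alongside the wireless one. After vaginal birth the wireless sensors come first ("will be immediately placed on the newborn"), and "the standard of care wired monitoring system (Infinity Monitor, Drager) will be placed on the newborn after 10-20 min of age". At C-section, "the infant will be randomized for the type of monitoring system to be applied first", and the other system follows at the same 10-20 minutes. Recording runs to 2 h of age. The data collection form (Appendix 1, part 3) records the order.

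**Survey.** Under Section 3.3.4, parents are "asked to complete a short survey to after the sensors of both systems are removed". Appendix 2 divides the parent survey into "Section 1: Your experience with the Wired Monitoring" and a matching second section on the wireless system. Nothing tells parents how to allow for the other system being on the baby at the same time.

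**Analysis.** Aim 1d in Section 2.2 is a descriptive analysis of the surveys and of satisfaction with the wireless system. The sentence introducing Aim 1 says its outcomes are measured for both systems. Section 4 does not mention the survey. Section 2.2 lists C-section versus vaginal delivery as a subgroup for wireless feasibility, but no analysis by order of application is planned.

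**The concern.** The survey is laid out as if parents had two separate experiences. By design they had one, mostly combined. A parent who reports too many stickers, or that adhesives and sensors get in the way of bonding, is describing a baby who wore two chest adhesives and two limb sensors. The parent's opinion of the wireless sensors was likewise formed with the wires attached.

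Aim 1d is one of four feasibility outcomes, and the purpose in Section 2.3 stresses that the technology is non-intrusive. Percentages from the two survey sections set side by side will be read as wired versus wireless, even if they are labelled descriptive. At stake is what the trial can say about parents' acceptance of each system. Its coverage and agreement results are not affected.

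**Working it through.** The plan gives no sample size or precision for the survey, so there is no stated figure to reproduce. The check has three parts.

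**1. Wear time from the schedule.** Inputs from Section 3.3.3: a 120-minute window, with the second system added at g = 10 to 20 minutes. Assumptions: the first system goes on at about 0 minutes and both come off together at the end (the order of removal is not stated).

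Share of time with both on = (120 − g)/120: g = 10 gives 110/120 = 92%; g = 20 gives 100/120 = 83%.

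| Group | Wired alone | Wireless alone | Both on |
|---|---|---|---|
| Vaginal birth | 0 min | 10-20 min | 100-110 min |
| C-section, wireless first | 0 min | 10-20 min | 100-110 min |
| C-section, wired first | 10-20 min | 0 min | 100-110 min |

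**2. How many infants have any wired-only time.** The C-section share c and the allocation ratio are not given. Assuming 1:1 allocation, the share is c/2: c = 20% gives 10% (60 of 600); c = 50% gives 25% (150 of 600). So 75-90% of infants have none.

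**3. Survey items set against the schedule.**

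- *General wording, open to carry-over:* overall satisfaction, where only the section heading ties the question to the wired system; too many stickers; difficulty touching the baby, which mentions stickers as well as wires; and the bonding item, which lists adhesives and sensors along with wires and monitors.
- *In between:* the skin-lesion options. The question names the wired system, but the options refer to chest adhesives and a limb probe, and the wireless system also has a chest adhesive and a limb sensor.
- *Attributable by wording:* wires around or tangled on the baby, and wires or cables soiled or disconnected. The skin-to-skin item ("The monitors and wires interfere with my ability to do skin-to-skin (Kangaroo) care") also leans this way, because it mentions wires and not adhesives. In survey Section 2, several items ask about the wireless chest and limb sensors by name.

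Overall satisfaction is asked only for the wired system, and the two sections share no matched item and scale. A like-for-like comparison would be missing even without shared wear.

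**Precision of a contrast between the randomised C-section orders.** Take 600 × 0.96 = 576 infants, applying the 4% drop-out in Section 4, which comes from phase 1a recordings and not from surveys. Each order then has 576 × c/2 infants: about 58 at c = 20% and 144 at c = 50%. The 95% half-width for a difference of two proportions near 50% is 1.96 × √(0.5/n):

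- n = 144: 1.96 × 0.0589 = 11.5 percentage points
- n = 58: 1.96 × 0.0928 = 18.2 percentage points

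This assumes that all parents respond and ignores clustering by site.

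**The case against.** The strongest reply is that the parent survey is descriptive. No test or estimate of wired versus wireless opinion is planned from it, and the explicit wording about comparing the systems in Section 3.3.4 belongs to the health professionals' survey. Simultaneous wear is also deliberate, since the study needs paired signals from the same infant. Both points are correct. They limit the importance of the matter but do not remove it, because Aim 1 says its outcomes are measured for both systems and the survey asks for a separate experience of each.

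A reader might infer that no parental opinion can be assigned to either system. The documents do not support that: the items naming wires or cables, and those naming the wireless chest or limb sensor, can be assigned by their wording.

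A reader might also infer that the schedule favours the wireless system, because it has time alone in every vaginal birth and the wired system has none. That asymmetry is real, but the bias is not shown. Wireless sensors may worsen wired ratings, and wires attached for 83-92% of the time may worsen wireless ratings. Some survey Section 2 items ask what a wireless system might do and do not rate the wear itself.

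Finally, a contrast built only on recalling 10-20 minutes after a C-section would be a weak main result. Parents would answer about 100 minutes later, having by then experienced both systems, and the documents do not say what contact they have with the baby in that interval. This objection stands, and such a contrast should be supportive only.

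**Conclusion.** The concern holds in a limited form. One survey after 83-92% shared wear, with wired-only time scheduled only in wired-first C-sections, means that the general items in survey Section 1 may reflect both sets of sensors. Ratings in survey Section 2 carry the same limitation in the other direction. The net direction and size of any bias are unknown. Total loss of attribution, or a demonstrated advantage to the wireless system, would go beyond the documents.

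The wear-time figures rest on the Section 3.3.3 schedule and on both systems being removed together. The 10-25% of infants with wired-only time rests on an assumed C-section share of 20-50% and 1:1 allocation. The precision of about 12-18 percentage points adds full survey response and no site clustering. It is worth correcting because it changes what Aim 1d can conclude, at little cost.

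**What to change.** - **Reword the general items** in survey Section 1 so that each refers to one system only, for example the stickers of the wired system.
- **Report parent ratings by delivery mode and by the order recorded in Appendix 1**, for both survey sections. Show the two randomised C-section orders as a descriptive contrast.
- **Describe pooled general ratings as obtained with both systems worn together**, make no wired-versus-wireless claim from them, and state simultaneous wear as a limitation of Aim 1d.
- **Optionally, add one or two items** about the minutes before the second system was placed, worded identically whichever system came first. Treat these as a supportive result and not as the main Aim 1d result.

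The cost is slightly longer wording, translation for the sites, and a more limited claim. No extra infants are needed and the monitoring schedule does not change.

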2.2 Aims

Healthcare technology assessment is the multidisciplinary evaluation of medical technologies with regard to **feasibility, safety, efficacy**, indications for use, cost, and cost-effectiveness. A complete assessment should explore the scientific, ethical, economic, and social reasons for adopting a technology and it may influence the quality of service and distribution of resources.

In this multicenter study, we aim to assess the first 3 important criteria.

Aim 1 – To determine the **feasibility** of using a wireless system immediately after delivery and for the first 2h of age, while in the obstetrical center under unsupervised parents' care. The following outcomes will be measured for both wired and wireless systems:

- a. Percentage of time for which HR, RR, SpO₂ and T_{skin} data are displayed.
- b. Occurrence of gaps in signal detection/recordings (% and length).
- c. Causes of the gaps in signal detection/recordings.
- d. Descriptive analysis of user surveys and their satisfaction with the wireless system.

Aim 2 - To investigate the **safety** of using this wireless system immediately after delivery and for the first 2h of age. The following outcomes will be measured for both wired and wireless systems:

- a. Skin score to be determined by a blinded dermatologist using de-identified pictures of the skin after removal of the sensors of each system.
- b. Pain scale to assess any discomfort or pain during the removal of the sensors.
- c. Clinically significant events detected by the wired system (HR < 100 bpm or SpO₂ < 80%) but missed by the wireless system.

Aim 3 – To assess the **accuracy** of this wireless system in measuring HR, RR, SpO₂ and T_{skin} signals compared with the “standard of care” wired system. The following outcomes will be computed:

- a. Correlation coefficient
- b. Slope
- c. Variance accounted for
- d. Bias

Further subgroup analyses will be conducted to assess for systematic differences in feasibility, safety, and accuracy of the wireless system between the following:

- High vs. Low and Middle income countries
- Female vs. Male subjects
- Term vs. Preterm (born < 37 weeks gestational age) infants
- C-section vs. Vaginal delivery

- Skin pigmentation

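### Six survey tick-lists give answers that cannot be interpreted: two wireless-impact lists name no worsening and leave safety without a direction, and four problem or concern lists have no null option

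*Combined protocol and SAP*

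**What the plan says.** Section 2.2 makes the surveys outcome (d) of Aim 1: "Descriptive analysis of user surveys and their satisfaction with the wireless system". Section 3.3.4 says that the HCP survey is to find out how staff felt about the wireless sensors relative to their experience of the wired system. Section 5.1 provides for no data safety committee, but has the lead site carry out interim safety evaluations after 200 and 400 patients, and HCP survey responses are among the data reviewed. Section 4 does not mention the surveys, so it gives no denominator and no rule for blank answers.

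The forms are in Appendix 2.

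- **Wireless impact.** HCP item 13 asks "What do you think it might be the impact of a using a wireless system immediately after birth". The parent survey has a parallel item on the baby's hospital experience. Each lists five improvements (the parent list opens with "Easier Kangaroo care (KC) initiation"), then "Newborn safety", then a none option and a free-text option.
- **Wired problems.** The parent survey asks "What kind of problems have you seen with the use of the wired monitoring system", and HCP item 5 asks staff much the same. Each lists problems and a free-text option, and nothing else.
- **Wireless concerns, HCP items 11 and 12.** These list concerns about the chest and limb sensors plus free text. The matching wired question, HCP item 2, includes "I do not have concerns", and the parent wireless concern lists also have a no-concerns box.

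**The concern.** A tick-list can report only what its options distinguish, and two distinctions are missing here.

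The first is direction. On the two impact lists, a respondent who thinks the wireless system would shorten kangaroo care or disturb sleep has no box for it and must write it in. On safety, a respondent who expects a safer baby and one who expects a less safe baby tick the same box.

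The second is the meaning of a blank. Where a list has no null option, a respondent who saw no problem or has no concern leaves it empty, as does one who skipped the question. Neither ambiguity can be resolved from the list itself once the forms are collected.

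What is at stake is the reading of part of a named outcome, the wired-against-wireless comparison that the HCP survey is meant to support, and the HCP material that goes into the interim safety evaluations.

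**Working it through.** The plan gives no figure to reproduce. The check is a count of response options in Appendix 2, followed by what a count of ticks can and cannot identify.

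**Option counts**

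| List | Named options | Null option | Free text |
|---|---|---|---|
| Parent, wireless impact | 5 better, 0 worse, 1 undirected | yes | yes |
| HCP item 13, wireless impact | 5 better, 0 worse, 1 undirected | yes | yes |
| Parent, wired problems seen | 11 | **no** | yes |
| HCP item 5, wired problems seen | 10 | **no** | yes |
| HCP item 11, wireless chest concerns | 7 | **no** | yes |
| HCP item 12, wireless limb concerns | 8 | **no** | yes |
| *Comparison:* HCP item 2, wired concerns | 7 | yes | yes |
| *Comparison:* parent, wireless concerns (each sensor) | 6 | yes | yes |

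The comparison rows show that null options are used elsewhere in the same surveys, so their absence from the four lists is inconsistent.

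**Safety option.** Let s be the share ticking it. The share meaning safer can lie anywhere from 0 to s, and the share meaning less safe is the remainder. The net opinion is therefore known only to lie between −s and +s.

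**Blanks.** Let u be the share of returned surveys with the list left empty. The share who had nothing to report lies between 0 and u. If a problem is ticked on a share p of all returned surveys, its frequency among those who really answered lies between p (every blank means none) and p / (1 − u) (every blank is non-response).

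The documents give neither u nor p. As an illustration only, take p = 5%:

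| Share ticking anything (1 − u) | Lower limit p | Upper limit p / (1 − u) |
|---|---|---|
| 50% | 5% | 0.05 / 0.50 = 10% |
| 20% | 5% | 0.05 / 0.20 = 25% |
| 10% | 5% | 0.05 / 0.10 = 50% |

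The fewer people tick anything, the wider the gap. The study enrols low-risk infants for two hours, so a small ticking share on the wired problem lists is plausible, but that is an assumption.

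**The case against.** The strongest reply is that the surveys as a whole do let people speak against the wireless system. Parents rate their worry about its safety and accuracy for each sensor, tick named concerns, and rate its effect on bonding on a scale that runs from negative to positive. Staff can say that they are skeptical (items 7 and 8) or very concerned (items 9 and 10), and can tick safety by name in items 11 and 12. Staff are also asked for the benefits of the wired system (item 3). All of this stands. It rules out three inferences that a reader might draw:

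- *That perceived harm from the wireless system can appear only as free text.* This is true within the two impact lists, not across the surveys.
- *That the surveys favour the wireless system whatever users think.* Both impact lists offer none and free text. The missing null box in items 11 and 12 runs, if anything, against the wireless system. The net direction is not shown.
- *That the Aim 1 survey percentages are fixed by the options offered.* The aim promises a descriptive analysis and states no percentage, denominator or threshold. Most of the survey items are not affected.

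The reply on blanks is only partly right. Items 11 and 12 ask for concerns only if there are any, which gives a blank some meaning. Neighbouring answers can show that a survey was not abandoned, and returned surveys can be counted. But a respondent may answer the neighbouring items and still skip one list, so ambiguity remains.

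Nor do the other items fully repair the safety option. The bonding scale is in the parent survey only, and HCP items 9 and 10 print the same label on both sides of neutral, although their most concerned end is usable.

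**Conclusion.** The point holds for six tick-lists. Two impact lists name no worsening and carry a safety option that cannot be read in either direction. Four problem or concern lists leave blanks that cannot be separated from non-response. The option counts are exact. The size of the effect on any reported percentage is not known, because it depends on how many respondents leave a list empty and on how blanks are tabulated, and the documents give neither. The 10% to 50% upper limits above illustrate the mechanism and do not predict results.

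The consequence is limited. Aim 1(d) is one of four feasibility outcomes, no sample-size figure rests on it, and the Aim 2 safety outcomes are skin score, pain and missed events. The change should still be made, because the ambiguity cannot be removed after collection, HCP answers are read in the interim safety evaluations, and the correction is cheap.

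**What to change.** 1. In the parent impact item and HCP item 13, split the safety option into safer and less safe, and add the worsening counterpart of each of the five improvements. Alternatively, use one row per outcome answered worse, no change or better.
2. Add a box for no problem seen to the parent wired problem list and to HCP item 5.
3. Add a box for no concerns to HCP items 11 and 12.
4. State in Section 4 that each survey percentage is taken over all returned surveys, with item non-response shown separately.

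The cost is edits to the paper forms, the REDCap fields and the translations, and a slightly longer survey for parents shortly after a birth. Splitting the options adds less length than a full grid. Surveys already collected on the existing forms would have to be tabulated separately. No clinical procedure changes.
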